8.3.5. Sensitivity Analyses of the Secondary Analysis

For the mITT population, baseline and 12-month log transformed IgE and IgG4 will be modeled using a linear mixed model that will include a random intercept and fixed effects for each treatment arm, site, and an interaction term between treatment arm and time of measurement. Similarly to the ANCOVA, geometric least square means (LSmeans) and associated SEs will be presented for each treatment group. The geometric least square mean ratio comparing treatment vs placebo group, associated 95% confidence interval (CI) and p-value will be presented.

8.3 Other Endpoints

8.4.1 Exploratory Endpoint 1

Variable: CASI score over the 2 assessments occurring between 10 and 12 months of treatment

Analysis: Analyzed using a mixed effect repeated measures model looking at the CASI assessments at 10 and 12 months of treatment. The mixed model will include fixed effects for treatment group, baseline CASI score at randomization, site as well as a within-subject random effects. Treatment group differences will be tested using the F statistics from the mixed model with Kenward-Roger degrees of freedom. Least squares estimates of the CASI for both of the study arms will be obtained from the model and presented. Ninety-five percent confidence intervals for the estimated treatment effect (LS Mean for the German Roach arm – LS Mean for the Placebo arm) will also be obtained using the fitted-regression model. The validity of model assumptions will be explored using regression diagnostics and may include separate models to assess possible modification of the treatment effect by CASI or other fixed effects. In addition, for each subject, the average CASI overall assessments will be computed and summarized by treatment group (mean, standard deviation, median, minimum and maximum). For each visit where CASI is collected

following the first injection of study drug, summary statistics will be presented by treatment arm.

8.4.2 Exploratory Endpoint 2

Variable: Change in mean sneeze score after 12 months of treatment with cockroach SCIT.

Analysis: The comparison between arms will be conducted using an analysis of covariance (ANCOVA) model, where the change from baseline to 12-month mean sneeze score is the outcome. The ANCOVA model will include fixed categorical effects for treatment and baseline mean sneeze score, with adjustment for site. Least square means (LSmeans) and associated SEs will be presented for each treatment group. The comparison between treatment groups will be presented using the LSmeans difference and associated 2-sided 95% confidence interval (CI) and p-value.

8.4.3 Exploratory Endpoint 2

Variable: Additional asthma severity outcome measures

Analysis: The same mixed effect repeated measures model as used for the CASI, with the same covariates, will be used to examine treatment differences in the additional asthma severity endpoints:

1. Number of days with asthma symptoms (wheezing or tightness in the chest or cough)
2. Number of nights with asthma symptoms (waking up because of wheezing or tightness in the chest or cough)
3. Number of days with albuterol use
4. Number of nights with albuterol use
5. Asthma treatment step (medication requirements)
6. Asthma exacerbations

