7.4.1 Definition and Management of Acute Exacerbations

Consistent with NAEPP 2007 guidelines, study clinicians caring for participants in the Protocol ICAC-28 CRITICAL study will start a course of corticosteroids for severe and/or unresponsive exacerbations of asthma. For the purposes of the proposed analyses, an asthma exacerbation is defined as a prescription of a course of systemic steroids by a clinician or initiation of a course of systemic steroids by a participant or a hospitalization to prevent a serious asthma outcome. If a participant initiates and completes a course of systemic steroids without clinician involvement, this course will be counted only if the study clinician agrees the treatment was warranted and it meets the following dosage: the course for prednisone, prednisolone, or methylprednisolone will be at least 20 mg daily for 3 of 5 consecutive days. The course for dexamethasone will be a single daily dose. Study clinicians will strongly consider initiation of corticosteroids if:

- Albuterol is needed by inhaler (with or without a spacer) or by nebulization for more than 6 individual treatments in 24 hours; or
- Moderate-severe wheeze, cough, shortness of breath, and/or chest tightness or pain occurs for at least 5 of the preceding 7 days; or
- Symptoms of wheeze, cough, shortness of breath, and/or chest tightness or pain severe enough to place a participant in his or her “Red Zone” on their Asthma Action Plan (see Section 7.1.1.4) do not significantly improve after 3 doses of albuterol. (In such situations, in addition to the initiation of oral corticosteroids, the study clinician should consider directing the participant to the nearest ED.); or
- There is an unscheduled visit for acute asthma care requiring repeated doses of albuterol (clinician office, urgent care, ED); or
- Hospitalization is needed for asthma.

Permissible drugs for systemic corticosteroid treatment of asthma exacerbations include: prednisone, prednisolone, methylprednisolone, and dexamethasone. The course for prednisone, prednisolone, or

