13.4.5 Analyses of Exploratory Endpoints

13.4.5.1 CASI outcome measures

To account for the correlation among repeated measures within subject, the effect of cockroach SCIT on asthma severity will be analyzed using a mixed effect repeated measures model looking at the CASI assessments at 10 and 12 months of treatment.

The mixed model will include fixed effects for treatment group, baseline CASI score at randomization, site as well as a within-subject random effects. Treatment group differences will be tested using the F statistics from the mixed model with Kenward-Roger degrees of freedom. Least squares estimates of the CASI for both of the study arms will be obtained from the model and presented. Ninety-five percent confidence intervals for the estimated treatment effect (LS Mean for the German Roach arm – LS Mean for the Placebo arm) will also be obtained using the fitted-regression model. The validity of model assumptions will be explored using regression diagnostics and may include separate models to assess possible modification of the treatment effect by CASI or other fixed effects.

In addition, for each subject, the average CASI overall assessments will be computed and summarized by treatment group (mean, standard deviation, median, minimum and maximum). For each visit where CASI is collected following the first injection of study drug, summary statistics will be presented by treatment arm.

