7. FEV1

8.4.4 Exploratory Endpoint 3

Variable: Rhinitis severity outcome measures

Analysis: The same mixed effect repeated measures model as used for the CASI outcomes, with the same covariates, will be used to examine treatment differences in the secondary rhinitis severity endpoints:

1. Modified Rhinitis Symptom Utility Index
2. Rhinitis treatment step (medication requirements)

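### The FEV1, symptom, albuterol, treatment-step and rhinitis models adjust for baseline CASI instead of each outcome's own baseline: a minor loss of precision that costs nothing to avoid

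*SAP*

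**What the plan says.** SAP 8.4.1 defines the CASI analysis as a "mixed effect repeated measures model looking at the CASI assessments at 10 and 12 months of treatment". Its terms are listed in one sentence: "The mixed model will include fixed effects for treatment group, baseline CASI score at randomization, site as well as a within-subject random effects". Protocol 13.4.5.1 gives the same list.

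SAP 8.4.3 then applies "The same mixed effect repeated measures model as used for the CASI, with the same covariates" to seven asthma outcomes: days and nights with symptoms, days and nights with albuterol, treatment step, exacerbations and FEV1. SAP 8.4.4 applies "The same mixed effect repeated measures model as used for the CASI outcomes, with the same covariates" to the Modified Rhinitis Symptom Utility Index and the rhinitis treatment step. Protocol 13.4.5.3 and 13.4.5.2 match.

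On inference, SAP 8.4.1 says: "Treatment group differences will be tested using the F statistics from the mixed model with Kenward-Roger degrees of freedom". Item 6 of the asthma list is "Asthma exacerbations". Protocol 7.4.1 makes this an event: "an asthma exacerbation is defined as a prescription of a course of systemic steroids by a clinician", with participant-initiated courses and hospitalisation also counted.

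**The concern.** The CASI model contains a single baseline term, and it is CASI. If the covariates really are the same, FEV1 at months 10 and 12 is adjusted for baseline CASI and not for baseline FEV1, and the rhinitis index is adjusted for an asthma score. An outcome's own earlier value is usually its best single predictor, so this choice tends to leave explainable variance in the residual.

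Precision is what is at stake. Accrual is about 80, and the power statement in Protocol 13.6 is for 54. Protocol 13.1 counts an effect on asthma severity measures among the major secondary hypotheses, although Protocol 3.4 lists all these outcomes as exploratory. Wider intervals than necessary make a small trial harder to read.

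**Working it through.** **Is the wording literal?** In its other baseline-adjusted models the SAP uses the outcome's own baseline: mean TNSS (8.2.2), TNSS AUC (8.3.2), IgE and IgG4 (8.3.4), mean sneeze score (8.4.2), the mechanistic measures (8.4.5) and sneeze AUC (8.4.6). Sections 8.3.4 and 8.4.5 refer to the respective baseline. Sections 8.4.3 and 8.4.4 do not, so a programmer following the text would enter baseline CASI. SAP section 2 gives the SAP precedence over the protocol, and the protocol says the same here anyway.

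**Are own baselines available?** Yes. Protocol 3.1 has lung function and the asthma and rhinitis questionnaires administered from Screening. Appendix A shows spirometry, symptom questionnaires and concomitant medication at both Screening and Randomization. The asthma step is assigned at Screening and reviewed at Randomization (Protocol 7.1.1).

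**The plan's own figure.** The documents give no power, SD or correlation for these outcomes. The only related figure is 83% power for the primary endpoint in Protocol 13.6. It reproduces: with 27 per arm, a difference of 2.95 × 0.30 = 0.885 (2.95 is the placebo mean in the protocol's code), SD 1.09 and two-sided 0.05, the two-sample t-test has power 0.833. It is used below only to set the scale at 54 participants.

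**Precision.** Let r_own and r_CASI be the correlations of an outcome, averaged over months 10 and 12, with its own baseline and with baseline CASI. Adjusting for one covariate leaves residual variance proportional to 1 − r², so

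variance ratio (planned ÷ own baseline) = (1 − r_CASI²) ÷ (1 − r_own²).

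The power column takes an effect for which the own-baseline model has 80% power with 27 per arm: power = Φ(2.802 ÷ √ratio − 1.960), where 2.802 = 1.960 + 0.842. All correlations are assumptions.

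| r_own | r_CASI | Variance ratio | SE ratio | 54 ÷ ratio | Power |
|---|---|---|---|---|---|
| 0.3 | 0.3 | 0.91/0.91 = 1.00 | 1.00 | 54.0 | 80% |
| 0.3 | 0 | 1/0.91 = 1.10 | 1.05 | 49.1 | 76% |
| 0.5 | 0.3 | 0.91/0.75 = 1.21 | 1.10 | 44.5 | 72% |
| 0.5 | 0 | 1/0.75 = 1.33 | 1.15 | 40.5 | 68% |
| 0.7 | 0.5 | 0.75/0.51 = 1.47 | 1.21 | 36.7 | 64% |
| 0.7 | 0 | 1/0.51 = 1.96 | 1.40 | 27.5 | 52% |

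If r_CASI exceeded r_own the ratio would fall below 1 and the planned covariate would be the better one.

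**Exacerbations.** F statistics, Kenward-Roger degrees of freedom and least squares means describe a linear mixed model. That is an inference, since the SAP names no distribution. Table 7.1.1.2a of the protocol counts steroid courses since the last medication visit and those visits are two months apart, so two assessments cover about 4 of 12 months.

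A simulation of 4,000 trials per scenario assumed 0.3 to 1.0 events per year, dispersion 1 and a constant effect. The linear analysis was a t-test on each participant's two-visit mean, without site or baseline terms.

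- With no treatment effect, 86 to 95% of two-visit observations are zero, and the linear test rejects in 4.4 to 5.6% of trials.
- At a rate ratio of 0.5, linear-test power is 6 to 17% (27 per arm) or 10 to 24% (40 per arm).
- An overdispersed Poisson test on the same two visits has 0.1 to 10% (27 per arm) or 0.6 to 21% (40 per arm). It was conservative here, so this shows no gain rather than ruling one out.
- The same Poisson test over 12 months has 8 to 32% or 19 to 47%.
- At a rate ratio of 0.5, the linear 95% interval for the active-arm mean extends below zero in 72 to 92% (27 per arm) or 57 to 89% (40 per arm) of trials.

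**The case against.** The strongest reply is that little depends on these models. All are exploratory, SAP 8.1.4 calls the study a pilot, and CASI itself is adjusted for its own baseline in 8.4.1. That stands, and it sets the severity. A reader might infer that the trial's clinical asthma evidence comes only from the affected outcomes; the CASI analysis shows that it does not.

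The size is also uncertain. Protocol 2.4 speaks of components of CASI, so some asthma outcomes may share much of their variance with baseline CASI. Entry requires FEV1 of at least 80% predicted and an asthma control score of at least 20 (Protocol 4.2), which narrows the baseline range and may weaken r_own. Both points argue for the lower rows of loss for some outcomes. A single percentage would claim more than the documents support.

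On exacerbations, a reader might infer that the linear model invalidates the test. The simulation does not show this: type I error held. A reader might also infer that months 10 to 12 is the wrong window. It can be defended, because escalation may take up to 40 weeks (SAP 7.3; Protocol Appendix A) and a late window aims at the maintenance effect. The 12-month power gain assumes a constant effect and is therefore optimistic. What remains is scale: a difference in arm means, with limits that can fall below zero, is an awkward summary of rare events. The diagnostics planned in 8.4.1 have no named fallback.

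**Conclusion.** The point holds as a free improvement of minor severity. Taken as written, FEV1, symptom days and nights, albuterol days and nights, asthma treatment step and both rhinitis outcomes are adjusted for baseline CASI although their own baselines are collected.

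A reader might take this as bias or as uncorrected imbalance that distorts the comparison. The documents do not support that: allocation is randomised 1:1, so adjusting for a different baseline variable leaves the treatment estimate unbiased and affects only its precision.

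The variance ratio is 1.00 to 1.10 with own-baseline correlation 0.3 (CASI correlation 0.3 to 0), 1.21 to 1.33 with 0.5 (0.3 to 0), and 1.47 to 1.96 with 0.7 (0.5 to 0). The loss is probably smallest for CASI components and largest for FEV1 and rhinitis. That ordering is a judgement, since the documents give no correlations.

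The exacerbation model is a secondary suggestion about scale and clarity, not a demonstrated error.

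**What to change.** In SAP 8.4.3 and 8.4.4, replace the reference to shared covariates with: *treatment group, site and the respective baseline value of each outcome as covariates*. State that baseline is the last pre-treatment value, in line with SAP 6.2. The number of model terms does not change and no new data are needed. The cost is one line in each section.

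Optionally, give exacerbations their own short paragraph. It would specify a count per participant, a negative binomial or robust Poisson model, log follow-up time as offset, and an any/none analysis if events are few. The offset also lets participants who leave early contribute, which matters because Protocol 11.2.2 allows termination for repeated steroid bursts. The paragraph should state the period and the reason for it: the late window targets maintenance, while the whole treatment period gives more events but includes escalation. If prior courses are used as a baseline term, note that Protocol 4.3 truncates that history at entry (no more than 2 courses in 12 months and none in the last 3). The cost is one extra model, and site terms may need to be dropped if events are sparse.

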7. FEV1

8.4.4 Exploratory Endpoint 3

Variable: Rhinitis severity outcome measures

Analysis: The same mixed effect repeated measures model as used for the CASI outcomes, with the same covariates, will be used to examine treatment differences in the secondary rhinitis severity endpoints:

1. Modified Rhinitis Symptom Utility Index
2. Rhinitis treatment step (medication requirements)

8.4.5 Exploratory Endpoints 4-9

Variable: Changes in component allergens, including Bla g 1, Bla g 2, Bla g 4, Bla g 5, and Per A 1, change in cockroach-specific blocking antibodies, Change in cockroach-specific blocking antibodies, Change in cockroach skin test reactivity, Changes in cockroach-specific T cell response, Changes in PBMC gene expression response to CR stimulation, Changes in nasal lavage gene expression

Analysis: Continuous variables with baseline value and one post-baseline measurement (12-months) will be analyzed and reported similarly to Secondary Endpoint 3 (Section 8.3.4, ANCOVA technique). Binary variables with baseline and post-baseline measures will be analyzed using logistic regression analyses. Models will contain 12-month measures as the outcome and factors for treatment arm, site, and the respective baseline measure as covariates. Odds ratios and 95% CI for the odds ratio of treatment group comparisons will be given.

8.4.6 Exploratory Endpoint 10

Variable: Sneeze score AUC at NAC-12 and NAC baseline. AUC will be calculated from sneeze score across 9 doses or until reaction (TNSS \geq 6 or sneeze score of 3, whichever occurs first).

Analysis: Sneeze score AUC will be calculated separately at baseline and 12 months for each subject using the trapezoidal rule. AUC will be calculated from sneeze score across 9 doses or until reaction (TNSS \geq 6 or sneeze score of 3, whichever occurs first). Change in sneeze score AUC will be compared between treatment arms using an analysis of covariance (ANCOVA) model. The model will contain 12-month sneeze score AUC as the outcome, and fixed effects for baseline sneeze score AUC, treatment group, and site. Least square means and associated SEs will be presented for each treatment group. Difference in least square means between treatment groups will be presented along with associated 95% confidence interval and p-value.

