8.1.5. Definitions of Outcome Measures

Many of the study endpoints derive from the nasal allergen challenge (NAC) procedure, where increasing doses of allergen are administered in defined time intervals (every 10-20 minutes) up to a specified maximum dose (up to 9 doses in ICAC-28) or a symptom threshold. After administration of each dose, staff count the number of sneezes for 10 minutes; five or more sneezes results in the maximum sneeze score of 3. After the 10 minutes have passed, participants rate their symptoms separately for runny nose, stuffy nose, and itchy nose on a scale of 0-3. The sum of the 4 symptoms is the Total Nasal Symptom Score or TNSS, which ranges from 0-12. In the ICAC-28 study, a NAC is considered positive when the TNSS ≥ 6 or the sneeze score = 3. The dose that elicits the positive response is called the NAC responsive dose. The baseline NAC is stopped at the responsive dose. The 12-month NAC is continued to its responsive dose or the baseline responsive dose, whichever is later.

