8.2.1. Computation of the Primary Endpoint

The primary endpoint of the study is the change in the mean TNSS from baseline to 12 months, calculated as the difference between the mean TNSS at baseline up to their baseline responsive dose and the mean TNSS at 12 months up to their baseline responsive dose.

Below are a couple of examples describing the above calculations. The top row displays the participant's TNSS scores and bottom row displays the participants sneeze scores. The pink line is the measurement taken at baseline while the blue line is the measurement taken at 12 months.

1. Example

In this example, the participant reacted at baseline with sneeze at dose 6.

The baseline mean TNSS is calculated up to dose 6:

$$\frac{0 + 0 + 0 + 1 + 0 + 3}{6} \approx 0.7$$

The 12-month mean TNSS is calculated the same as the baseline mean:

[figure not shown]
$$\frac{2 + 0 + 0 + 0 + 0 + 0}{6} \approx 0.3$$

Then change in the mean TNSS from baseline to 12 months will be calculated as:

Page 20 of 40

$$0.3 - 0.7 = -0.4$$

2. Example

Unlike the participant in the example above, this participant reacted at baseline with TNSS, dose 4. However, the calculation of the mean and change in mean are similar.

The baseline mean TNSS is calculated up to dose 4:

$$\frac{4 + 4 + 3 + 9}{4} \approx 5$$

The 12-month mean TNSS is calculated the same as the baseline mean:

$$\frac{2 + 2 + 3 + 4}{4} \approx 2.8$$

Then change in the mean TNSS from baseline to 12 months will be calculated as:

$$2.8 - 5 = -2.2$$

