8.3.2. Endpoint 2a

Variable: Change in TNSS AUC from baseline to 12 months, calculated as the difference between the AUC TNSS at baseline up to their baseline responsive dose and the AUC TNSS at 12 months up to their baseline responsive dose.

Analysis: For the mITT population, like the rules referenced in section 8.2.1, the TNSS AUC will be calculated separately at baseline and 12 months for each subject using the trapezoidal rule and divided by their baseline reactive dose. Change in TNSS AUC will be compared between treatment arms using an analysis of covariance (ANCOVA) model. The model will contain the change from baseline to 12-month TNSS AUC as the outcome, and fixed effects for baseline TNSS AUC, treatment group, and site. Least square means and associated SEs will be presented for each treatment group. Difference in least square means between treatment groups will be presented along with associated 2-sided 95% confidence interval (CI) and p-value.

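### Sneeze-score AUC (SAP 8.4.6) is cut at each visit's own reaction dose, so a child who tolerates more allergen can score worse and one who reacts sooner can score better

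*SAP*

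**What the plan says.** SAP 8.4.6 (Exploratory Endpoint 10) states: "Sneeze score AUC will be calculated separately at baseline and 12 months for each subject using the trapezoidal rule". The upper limit is given as "AUC will be calculated from sneeze score across 9 doses or until reaction", where reaction means a TNSS of at least 6 or a sneeze score of 3. No divisor is named, and nothing links the 12-month limit to the baseline challenge. The analysis is an ANCOVA: "The model will contain 12-month sneeze score AUC as the outcome, and fixed effects for baseline sneeze score AUC, treatment group, and site". It reports LS means, their difference, a confidence interval and a p-value.

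The TNSS measures in the same SAP are built differently. The primary endpoint (8.2.1) uses "the mean TNSS at 12 months up to their baseline responsive dose". Secondary endpoint 2a (8.3.2) uses "the AUC TNSS at 12 months up to their baseline responsive dose", computed "using the trapezoidal rule and divided by their baseline reactive dose". In the estimand table (SAP 14.1), the nine-doses-or-reaction limit applies to TNSS AUC at baseline only. The 12-month visit has its own limit: the baseline reacting dose or a TNSS of 12, whichever comes first.

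On the challenge itself, SAP 8.1.5 says "The baseline NAC is stopped at the responsive dose", while the 12-month challenge runs to the later of its own and the baseline responsive dose. Protocol 8.1.5 lets the 12-month challenge end earlier at a TNSS of 12 or for intolerable symptoms. On the scale, "five or more sneezes results in the maximum sneeze score of 3", so a sneeze score of 3 is itself a reaction.

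The sneeze AUC is not in the protocol's exploratory list (3.4), the estimand table (SAP 14.1) or the list of changes (SAP 12). No other section corrects 8.4.6.

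**The concern.** An undivided area grows with its width. Here the width is the number of doses given before the child reacts at that visit, and immunotherapy is meant to increase that number. A smaller area should mean less sneezing, but a longer tolerated range can enlarge it and an earlier reaction can shrink it. The arm difference then mixes sneeze intensity with dose tolerance, and the two can pull in opposite directions. An effective treatment could be reported, with an interval and a p-value, as having made sneezing worse. For a child who reacts sooner, 8.4.6 also ignores the 12-month scores that are normally collected beyond that reaction, up to the baseline dose.

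**Working it through.** **Inputs.** The limits are those in SAP 8.4.6, 8.3.2 and 8.1.5. Sneeze scores run from 0 to 3, and a 3 ends the range. The SAP names no x-axis, so unit dose steps are assumed. All sneeze paths below are assumed, because the documents contain no sneeze AUC data.

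**Plan's own figure.** None exists for this endpoint. The first worked example in 8.2.1 does reproduce: (0+0+0+1+0+3)/6 = 0.67 and 2/6 = 0.33, given there as 0.7 and 0.3.

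**Formula.** AUC to dose k = Σ (s_j + s_{j+1})/2 for j = 1 to k−1. Every term is zero or positive. On one and the same path, stopping later can only raise or keep the AUC, and stopping earlier can only lower or keep it.

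**Bound.** A child whose first reaction is a sneeze score of 3 at dose 2 has AUC (s1 + 3)/2. Since s1 is at most 2 without an earlier reaction, the AUC lies between 1.5 and 2.5. A child with a steady score of 1 over nine doses and no reaction has 8 × 1 = 8.

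**Cases.** Assumed baseline 0, 0, 1, 3 (reaction at dose 4): 0 + 0.5 + 2 = 2.5, or 2.5/3 = 0.83 per interval.

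| 12-month sneeze scores | Meaning | AUC by 8.4.6 | Against 2.5 | AUC to dose 4 | Per interval (÷3) |
|---|---|---|---|---|---|
| 0,0,0,1,1,1,2,3 | reacts at dose 8 | 6.5 | larger | 0.5 | 0.17 |
| 0,0,1,1,1,1,1,3 | reacts at dose 8 | 6.5 | larger | 1.5 | 0.50 |
| 0,0,0,0,0,0,1,3 | pure shift to dose 8 | 2.5 | same | 0 | 0 |
| all 0 to dose 9 | no sneezing, no reaction | 0 | smaller | 0 | 0 |
| 0,3, then 3,3 | reacts at dose 2, continued to 4 | 1.5 | smaller | 7.5 | 2.50 |
| 0,1,3, then 3 | reacts at dose 3, continued to 4 | 2.5 | same | 5.5 | 1.83 |

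By the 8.4.6 rule, only the child who stops sneezing moves the right way. With the common range all six do.

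**The SAP's first example.** Baseline TNSS 0,0,0,1,0,3 with a sneeze reaction at dose 6 puts the baseline sneeze AUC at 1.5 (dose-4 point not a sneeze) or 2.5 (dose-4 point a sneeze). At 12 months TNSS is 2,0,0,0,0,0. Suppose this child then reacts by sneezing only at dose 9, with zeros between (assumed). The AUC by 8.4.6 is again 1.5 to 2.5, so three more tolerated doses do not show. To the baseline dose it is 0 to 1.0, below baseline.

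**Is the divisor the cause?** Take the first row of the table.
- Each visit divided by its own doses: 6.5/8 = 0.81 against 2.5/4 = 0.625.
- Each visit divided by its own intervals: 6.5/7 = 0.93 against 2.5/3 = 0.83.
- Both visits divided by the baseline dose: 6.5/4 = 1.625 against 0.625.

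All three are still reversed. Only changing the cut-off corrects the direction.

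**How often.** A simulation used assumed dose-response curves: three slopes, each with a right shift of 2 doses, a right shift of 4 doses, halved intensity, or a left shift of 2 doses.
- *Nine improvement scenarios.* Among children who tolerated more, the 8.4.6 AUC was larger in 21–77%, equal in 6–14% and smaller in 15–69%. Its mean rose in 6 of 9 (change −1.09 to +1.48). The mean AUC to the baseline dose fell in all 9.
- *Three worsening scenarios.* Among children who reacted sooner, the 8.4.6 AUC was smaller in 53–82% and larger in 12–34%. Its mean fell in all 3, while the mean AUC to the baseline dose rose in all 3.

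**Divisor when a challenge stops early.** Suppose 12-month scores 0, 3, stopped at dose 2 with TNSS 12. Dividing by the baseline dose as in 8.3.2 gives 1.5/4 = 0.375 against 0.625, an apparent gain. Dividing by intervals scored gives 1.5/1 = 1.5 against 0.83, a worsening. This removes the credit for a short path but does not settle every case: 0, 0, 3 stopped at dose 3 gives 1.5/2 = 0.75, just under 0.83.

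**The case against.** The strongest reply is that reversal is not built in. Added doses scored 0 contribute no area, a pure right shift leaves the AUC unchanged, and a strong responder who stops sneezing gets the best possible value. A reader might infer from 8.4.6 that every child who tolerates more scores worse and every child who reacts sooner scores better. The documents do not support that, because it depends on the scores at the added doses. This part of the reply stands.

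A reader might also blame the missing divisor, since 8.3.2 has one and 8.4.6 does not. That does not hold either: dividing alone leaves the direction reversed.

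It is also fair to say that the size of the effect comes from assumed paths, and that the measure is exploratory. Responsive dose is analysed on its own (8.3.3), symptom intensity to the baseline dose is covered by 8.2.1 and 8.3.2, and sneezing has a mean-score endpoint (8.4.2). An odd sign would be read beside these. This limits the stakes but does not make the rule sound.

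Finally, the common range can itself be cut short at 12 months by the early-stop conditions. That is correct, and it is why the divisor and an early-stop rule have to be written down.

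**Conclusion.** The concern holds as a possible, not a certain, reversal. The upper limit in SAP 8.4.6 is an outcome of treatment, so the sneeze-score AUC may rise, stay flat or fall when a child improves. On assumed paths from a baseline of 2.5, later reaction gave anything from 2.5 to 6.5 and reaction at dose 2 gave 1.5. Under the simulated curves the mean moved the wrong way in 6 of 9 improvement scenarios and in all 3 worsening ones. These figures rest on unit dose steps and assumed sneeze curves. They show a range, not an expected size.

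A reader might go further and doubt the trial's main results. The documents give no ground for that: the primary endpoint and TNSS AUC already use the baseline responsive dose at both visits, and nothing confirmatory depends on Endpoint 10. The change is worth making because, as written, the LS-mean difference for this endpoint has no dependable sign.

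**What to change.** In SAP 8.4.6:

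- Compute the sneeze-score AUC at both visits up to the baseline responsive dose. Where a child reacts sooner at 12 months, use the scores already collected beyond that reaction.
- Divide by the number of dose intervals actually scored within that range, so that a 12-month challenge ended early (TNSS of 12 or intolerable symptoms) is not scored as an improvement merely because it is short. If only one dose was given, use that single score.
- State that the x-axis is dose number.
- Report by arm how many 12-month challenges ended before the baseline dose. As a sensitivity analysis, carry the last sneeze score forward to that dose. In the 0, 0, 3 case this gives 0, 0, 3, 3: (0 + 1.5 + 3)/3 = 1.5, above 0.83.

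The cost is SAP wording and reuse of the TNSS AUC code with a changed divisor. No new data are needed, because the 12-month challenge already runs to at least the baseline responsive dose unless it is stopped early.
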